9.4 Stent Thrombosis

Stent thrombosis will be defined according to ARC-2 criteria (35). Definition and timing of stent thrombosis (43):

Classification	Criteria
Definite stent/scaffold thrombosis	
Angiographic confirmation of stent/scaffold thrombosis*
 
The presence of a thrombus[†] that originates in the stent/scaffold or in the segment 5 mm proximal or distal to the stent/scaffold or in a side branch originating from the stented/scaffolded segment and the presence of at least 1 of the following criteria:
 
 Acute onset of ischemic symptoms at rest New electrocardiographic changes suggestive of acute ischemia Typical rise and fall in cardiac biomarkers (refer to definition of spontaneous myocardial infarction) 
Or
 
Pathological confirmation of stent/scaffold thrombosis
 
 Evidence of recent thrombus within the stent/scaffold determined at autopsy Examination of tissue retrieved following thrombectomy (visual/histology)
Probable stent/scaffold thrombosis	Regardless of the time after the index procedure, any myocardial infarction that is related to documented acute ischemia in the territory of the implanted stent/scaffold without angiographic confirmation of stent/scaffold thrombosis and in the absence of any other obvious cause [‡]
Silent stent/scaffold occlusion	The incidental angiographic documentation of stent occlusion in the absence of clinical signs or symptoms is not considered stent thrombosis.
Timing of ST (duration after stent implantation)	
Acute	0§–24 h
Subacute	>24 h–30 d
Late	>30 d–1 y
Very late	>1 y

Early stent thrombosis is 0 to 30 days (acute plus subacute stent thrombosis). MI indicates myocardial infarction.
 *Definite stent/scaffold thrombosis is considered to have occurred by either angiographic or pathological confirmation.
 †Occlusive thrombus: Thrombolysis in Myocardial Infarction grade 0 or 1 flow within or proximal to a stent/scaffold segment. Nonocclusive thrombus: intracoronary thrombus is defined as a (spherical, ovoid, or irregular) noncalcified filling defect or lucency surrounded by contrast material (on 3 sides or within a coronary stenosis) seen in multiple projections, persistence of contrast material within the lumen, or visible embolization of intraluminal material downstream.
 ‡When the stented/scaffolded segment is in the left circumflex coronary artery or in the presence of preexisting electrocardiographic abnormalities (eg, left bundle branch block, paced rhythms), definitive evidence of localization may be absent and Clinical Events Committee adjudication is based on review of all available evidence).
 §Defined as the moment the patient is undraped and taken off the catheterization table.

9.5 Stroke

Defined as the presence of a new focal neurologic deficit thought to be vascular in origin, with signs or symptoms lasting more than 24 hours. It is strongly recommended (but not required) that an imaging procedure such as CT scan or MRI be performed. Stroke will be further classified as ischemic, hemorrhagic or type uncertain.

9.6 Nonfatal Cardiac Arrest

Successful resuscitation from either documented or presumed ventricular fibrillation or ventricular tachycardia or asystole.

9.7 Contrast-induced Acute Kidney Injury (AKI)

Contrast-induced AKI is defined as any of the following:

- Increase in Serum Creatinine (SCr) by X0.3 mg/dl (X26.5 μmol/l) within 48 hours; or
- Increase in SCr to X1.5 times baseline, which is known or presumed to have occurred within the prior 7 days; or

- Urine volume ≥ 0.5 ml/kg/h for 6 hours

Staging of AKI is showed in the following Table.

Table 2 | Staging of AKI

Stage	Serum creatinine	Urine output
1	1.5–1.9 times baseline OR ≥ 0.3 mg/dl (≥ 26.5 μ mol/l) increase	< 0.5 ml/kg/h for 6–12 hours
2	2.0–2.9 times baseline	< 0.5 ml/kg/h for ≥ 12 hours
3	3.0 times baseline OR Increase in serum creatinine to ≥ 4.0 mg/dl (≥ 353.6 μ mol/l) OR Initiation of renal replacement therapy OR, In patients < 18 years, decrease in eGFR to < 35 ml/min per 1.73 m ²	< 0.3 ml/kg/h for ≥ 24 hours OR Anuria for ≥ 12 hours

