5.2 Main Secondary objectives

- To test if a functionally-driven complete revascularization is superior to a culprit only strategy in the reduction of POCE of all-cause death, any MI, any stroke, any revascularization at 3 and 5 years
- To test if a functionally-driven complete revascularization is superior to a culprit only strategy in the reduction of the device oriented composite endpoint (DOCE) of cardiovascular (CV) death, MI or non-culprit target vessel revascularization (TVR) at 1, 3 and 5 years
- To test if a functionally-driven complete revascularization is superior to a culprit only strategy in the reduction of the composite endpoint of cardiovascular death or MI at 1, 3 and 5 years
- To test if a functionally-driven complete revascularization is superior to a culprit only strategy in the reduction of the composite endpoint of death or MI at 1, 3 and 5 years
- To test if a functionally-driven complete revascularization is superior to a culprit only strategy in the reduction of all the single components of the POCE and DOCE at 1, 3 and 5 years
- To evaluate the rate of ischemic adverse events in patients interrupting DAPT
- To evaluate the rate of ischemic adverse events in patients disrupting DAPT
- To test if a functionally-driven revascularization is non-inferior to a culprit only revascularization strategy in Contrast-Induced Acute Kidney Injury (CI-AKI) rate

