6.2 Study flow chart

6.3 Screening

All patients undergoing CAA because of MI must be screened for eligibility. Patient's eligibility must be assessed after the evidence of multivessel disease at CAA amenable for PCI with a clear culprit lesion. After eligibility is confirmed, written informed consent must be obtained prior to randomization. Successful culprit lesion treatment must be obtained in all patients before randomization. The suggested stent for culprit lesion treatment is DES with degradable polymer. In STEMI setting, it is possible to enroll the patient also after the successful primary PCI due to the possible difficulty to obtain an informed consent in the setting of STEMI. Key baseline patient characteristics (i.e., inclusion/exclusion criteria, demographics, medical history, details of cardiovascular anatomy, ECG and laboratory test results) will be recorded on the electronic Case Report Forms (eCRF). All CAA from the initial qualifying PCI as well as all functional assessments will be collected and forwarded to an angiographic core lab for further assessment.

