8.1.7 Follow up

After initial hospital discharge, routine clinic follow-up will occur at 1 month \pm 14 days (telephone contact or clinic visit), 1 year (clinic visit) and yearly clinic visits thereafter up to 3 years. At each visit, clinical outcomes (death, MI, stroke, bleeding), compliance with medical therapy and smoking cessation, will be assessed. LDL, blood pressure and glycemic targets, anginal status (SAQ), quality of life (EQ-5D) and physical performance (SPBB) will be assessed at the 12-month and 3 year-follow-up visit.

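### CI-AKI is tested for non-inferiority, but the protocol text fixes no post-procedure creatinine, no pre-contrast baseline and no clock start, so detection rests on unscheduled tests in an open-label trial

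*Protocol*

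**What the plan says.** Protocol section 5.2 lists, among the main secondary objectives, a test that the functional strategy is "non-inferior to a culprit only revascularization strategy in Contrast-Induced Acute Kidney Injury (CI-AKI) rate".

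Section 9.7 counts a case if any one of three criteria is met:
- "Increase in Serum Creatinine (SCr) by X0.3 mg/dl" within 48 hours (the X evidently stands for an at-least sign, as in the staging table);
- a rise to 1.5 times baseline, "which is known or presumed to have occurred within the prior 7 days";
- "Urine volume ≥ 0.5 ml/kg/h for 6 hours".

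Section 9.7 does not define baseline and names no procedure from which the 48 hours run.

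On data collection, section 6.3 has unspecified laboratory results entered on the eCRF at screening. Section 8.1.7 places the first contact at 1 month ± 14 days after discharge, by telephone or clinic visit. At 12 months and 3 years, "LDL, blood pressure and glycemic targets, anginal status (SAQ), quality of life (EQ-5D) and physical performance (SPBB) will be assessed"; creatinine is not in that list.

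On exposure, section 6.4 randomizes after angiography and culprit treatment. Section 6.3 adds that "In STEMI setting, it is possible to enroll the patient also after the successful primary PCI". Section 8.1.2 bars further non-culprit PCI in the control arm. Section 8.1.3 lets the complete arm finish in the index procedure or later in the same admission.

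The trial is open-label (section 6.1). The outcomes listed for blinded adjudication in section 9.9 are death, MI, stroke and revascularization.

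**The concern.** The endpoint compares a creatinine value after contrast with one from before it. The protocol text secures neither. The first scheduled contact normally falls after both creatinine windows have closed, so ascertainment depends on whatever blood tests are done in hospital, by staff who can know the allocation.

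The reference value is equally loose. Every patient has had contrast before randomization, so a laboratory value recorded at enrolment may already be post-contrast, most clearly in STEMI patients enrolled after primary PCI. Because a staged complete-arm patient receives contrast again, one undefined baseline and one undefined clock cover different exposures in the two arms.

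Section 3.3 itself names CI-AKI as a possible drawback of complete revascularization in elderly patients, and this is the only renal comparison among the stated objectives. A non-inferiority statement on it would be read as reassurance. A later SAP can supply a margin, an effect scale or a missing-data rule. It cannot supply a blood sample that was never drawn.

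**Working it through.** **Available figures.** The protocol gives no rate, margin or power for CI-AKI, so nothing specific to this endpoint can be reproduced. The only planning figure used is the 1358 patients in section 10.1. That figure reproduces as a one-sided 5% comparison of 15% with 10.5% at 80% power: n per arm = [1.645·√(2 × 0.1275 × 0.8725) + 0.842·√(0.15 × 0.85 + 0.105 × 0.895)]² / 0.045², which rounds up to 679, and 2 × 679 = 1358.

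**Equal under-detection.** Let pc be the true control rate, m the margin on the risk difference, and s the fraction of true cases detected, the same in both arms. Set the true excess equal to m, the boundary at which non-inferiority should be declared only at the nominal rate. Then:
- observed rates: a = s·pc and b = s·(pc + m);
- observed difference: s·m;
- SD = √[a(1 − a)/679 + b(1 − b)/679];
- chance of a false declaration = Φ[(m − s·m)/SD − z].

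Example with assumed pc = 15%, m = 5 points and s = 0.8: a = 0.12, b = 0.16, SD = √(0.2400/679) = 0.0188. At one-sided 2.5%, Φ(0.010/0.0188 − 1.96) = Φ(−1.43) = 7.7%.

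Results for pc = 15% and m = 5 points:

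| Detected fraction s | Observed excess (points) | Observed risk ratio | False declaration, one-sided 2.5% | One-sided 5% |
|---|---|---|---|---|
| 1.0 | 5.0 | 1.33 | 2.5% | 5.0% |
| 0.8 | 4.0 | 1.33 | 7.7% | 13.3% |
| 0.6 | 3.0 | 1.33 | 22.5% | 32.9% |
| 0.4 | 2.0 | 1.33 | 58.2% | 70.0% |

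Ranges for control rates of 10% to 20%, one-sided 2.5%:
- 5-point margin: 6.9–8.9% at s = 0.8 and 18.9–28.8% at s = 0.6;
- 3-point margin: 4.8–5.7% at s = 0.8 and 9.7–13.9% at s = 0.6.

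The risk ratio column does not move, since b/a = (pc + m)/pc whatever s is.

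**Unequal detection.** Take equal true rates of 15%. With 60% detected in the control arm and 80% in the complete arm, the observed difference is 0.15 × 0.8 − 0.15 × 0.6 = +3 points, against non-inferiority. With the fractions exchanged it is −3 points, in favour of it.

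**Baseline timing.** In the control arm, no planned contrast follows randomization. A baseline drawn after the culprit PCI can therefore already include part of the rise and hide a case. In a staged complete-arm patient, the same sample still precedes the second exposure. That pattern would hide relatively more cases in the control arm.

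**Urine criterion.** The list in 9.7 counts output at or above 0.5 ml/kg/h for 6 hours as injury. The staging table below it uses output below 0.5. As printed, the list would capture patients whom the table does not stage, which is over-detection.

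**The case against.** **Direction of bias.** A reader might infer that kidney injury will be under-detected and non-inferiority therefore favoured. The documents do not support that as a general statement. It needs a risk-difference scale and similar detection in both arms. The protocol states no scale, and both scale and margin may properly be left to the SAP. More sampling around a second session, or a post-contrast baseline, would work against non-inferiority. The urine criterion as printed adds cases instead of losing them. This objection stands in full.

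**Length of stay.** A reader might also set the mean stays in section 3.3 (3.52 and 3.71 days) against 7 days and conclude that only about half the window is observable. That does not hold. The figures come from a cited STEMI cohort, whereas this trial enrols STE and NSTE MI patients aged 75 or over. The 7-day clause looks back at when the rise occurred and does not require sampling through day 7. A stay of 3.52 days is also 84 hours (3.52 × 24), longer than the 48-hour window.

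**Unseen material.** The 6.2 flow chart and the eCRF are not shown, so a laboratory time point there cannot be excluded. This stands as a limit, but sections 8.1.7 and 9.7 would still need to agree with such a time point, and 9.7 would still lack a baseline and a clock start.

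**Importance.** CI-AKI is one of eight main secondary objectives, and nothing marks it as the key secondary endpoint of the sequential procedure in section 10. The primary conclusion is untouched.

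**Conclusion.** The point holds in a limited form. The protocol commits to a non-inferiority test of CI-AKI without fixing, in its readable text, the samples, the reference value or the start of the window on which the definition depends. It is an open-label trial, and CI-AKI is not on the adjudication list. The result would partly reflect who was sampled and when.

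The size is illustrative only. On the difference scale, with equal detection of 80% or 60%, an assumed 15% control rate and a 5-point margin, a nominal 2.5% error becomes 7.7% or 22.5%; a 3-point margin gives smaller inflation. On the ratio scale, equal under-detection leaves the expected estimate unchanged. With unequal detection, the sign can go either way. All rates, margins and detection fractions are assumptions. The change should be made, but the matter is confined to this secondary claim.

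**What to change.** In section 9.7:
- Define baseline as the last creatinine before the index angiography, in both arms.
- State that the window starts at each in-hospital contrast procedure, and that values in each window are compared with that single baseline.
- Record in-hospital creatinine on the eCRF on the same schedule in both arms, for example within 48 hours after each procedure or at discharge if earlier, and use the peak value. A single sample after the last procedure would not do: in staged patients it could miss a rise after the culprit PCI that had resolved, and only the complete arm is staged.
- Reconcile the urine criterion with the staging table.

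Analyse all randomized patients, consistent with the intention-to-treat set in section 10, and handle missing creatinine by a stated sensitivity analysis. Restricting to patients with both values would select after randomization, losing early deaths and discharges.

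If common sampling cannot be required, report CI-AKI descriptively and drop the non-inferiority claim in section 5.2.

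The cost is protocol and eCRF wording and at most a routine blood test in patients already in hospital. Sampling at discharge when that comes first avoids a return visit, at the price of a shorter observed window for those patients. The descriptive fallback costs only the claim.

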10 STATISTICAL ANALYSIS PLAN

All statistical analyses will be performed by the Centro di Ricerca Clinica ed Epidemiologica of the University of Ferrara under the supervision of [name]. Analysis will be performed on an Intention to Treat (ITT) set, defined as all intentionally randomized patients, by randomization treatment. Supportive per-protocol analyses will be performed on the primary and key secondary endpoints. A detailed statistical analysis plan will be completed before the end of the study. In brief, continuous variables will be tested for normal distribution with the Kolmogorov-Smirnov test and with visual estimate of Q-Q plot. Normally distributed variables will be presented as mean±SD and compared by t test and 1-way ANOVA. Otherwise, median [inter-quartile range], Mann-Whitney U and Kruskal-Wallis tests will be used. Categorical variables will be summarized in terms of absolute and relative frequencies (percentages) and compared by using χ^2 test. One-sided tests will be done in order to check the superiority of functionally-driven complete revascularization. Statistical significance will be set at $\alpha=0.05$ level. Formal type-I error control will be ensured for the primary and the key secondary endpoint by a sequential procedure where significance for the key secondary endpoint is accepted only if the primary endpoint is positive. Kaplan-Meier curves will be plot to describe survival free from adverse events, and difference between groups will be test will log-rank test. The primary analysis will be based on events of all follow-up time of each patient at the time of the database lock. Further analyses will be performed with events after more than 30 days considered as censored, as well as after more than 365 days considered as censored. Any confounding factor will be tested by Cox regression models. Variables with a p-value <0.1 at univariate analysis will be entered into a multivariable analysis to identify the independent predictors. When appropriate, 95% CI will be calculated. In addition, we will assess the composite primary outcome POCE (all-cause mortality, any MI, any stroke and any revascularization) with the use of the Finkelstein–Schoenfeld method, which is based on the principle that each patient in the clinical trial is compared with every other patient in a pairwise manner. This method gives a higher importance to all-cause mortality. The pairwise comparison proceeds in hierarchical fashion, using all-cause mortality, followed by frequency of MI when patients cannot be differentiated on the basis of mortality and so on for the other endpoints We will apply the Finkelstein–

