10.1 Determination of sample size

Data regarding death, MI, stroke and revascularization at 1 year in patients ≥ 75 years with MI and multivessel disease treated with culprit only revascularization are lacking. Taking into account available data (see tables below) and our preliminary data coming from “The frailty in elderly patients receiving cardiac interventional procedures (FRASER) program”, we estimated a conservative 15% rate of the primary endpoint at 1 year in the culprit-only strategy group. Considering that functional assessment should reduce the primary endpoint of at least 30% (see table below), 1358 patients are required to have a 80% chance of detecting, as significant at the 5% level, a 30% difference in the primary outcome between the two groups considering a 15% rate of the primary endpoint in the control group. Considering a 2% attrition rate final sample size is inflated to 1385 patients. After at least 900 patients have completed the 30-day follow-up, the assumption of the sample size calculation will be checked by estimating the Kaplan-Meier 1-year risk of having reached the primary endpoint. Unadjudicated data will be used for this purpose. No randomization information will be available and all the evaluation on the sample size will be performed in a blinded fashion. If the pooled event rate will be considerably lower than expected the sample size may be increased.

Ischemic outcome at 1 year in patients with ACS treated with culprit-only revascularization

Study	MI	Repeat revascularization	MACE
Compare acute	4.7%	17.5%	20.5%
Culprit	2.7%	8.2%	21.2%
Prami	8.6%	19.9%	22.9%
Danami-3-Primulti	5%	9%	22%
Translate-ACS	7%	17%	22%

Primary endpoint reduction with functional guided revascularization in ACS setting

Study	Primary endpoint	HR
Compare acute	MACCE*	0.35 [0.22-0.55]
Danami-3-Primulti	all-cause mortality, reinfarction, or ischaemia-driven revascularisation	0.56 [0.38-0.83]

*all-cause mortality, nonfatal myocardial infarction, any revascularization, and cerebrovascular events.

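### The urine criterion in the CI-AKI definition (Protocol 9.7) runs opposite to its own staging table; applied literally, it would favour a false non-inferiority conclusion on kidney injury

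*Protocol*

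**What the plan says.** Section 9.7 opens its list with "Contrast-induced AKI is defined as any of the following", so each line is sufficient alone. Two lines concern serum creatinine. The third reads "Urine volume ≥ 0.5 ml/kg/h for 6 hours".

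The staging table below the list gives "< 0.5 ml/kg/h for 6–12 hours" as the urine criterion for stage 1. Stages 2 and 3 require low output for longer, lower output still, or anuria.

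The definition serves a main secondary objective in section 5.2: "To test if a functionally-driven revascularization is non-inferior to a culprit only revascularization strategy in Contrast-Induced Acute Kidney Injury (CI-AKI) rate". It is the only non-inferiority objective in that section. The protocol gives neither a margin nor an expected CI-AKI rate. Section 10 is a summary and promises a detailed statistical analysis plan.

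In the text available for this review, the creatinine lines carry a stray letter where a comparison sign belongs, for example "Increase in SCr to X1.5 times baseline". The urine line carries a clean, valid sign.

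**The concern.** The list and the table cannot both be right about direction. Under the list, preserved urine output over six hours makes a patient a case. Under the table, it is low output that counts.

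For a superiority comparison, adding false cases equally to both arms usually costs power. For a non-inferiority comparison it works the other way: it shrinks a real excess and makes the tested strategy easier to pass. Section 3.3 of the background names CI-AKI as a possible drawback of complete revascularization in the elderly, so this objective is there to detect a harm of the tested strategy. Section 9.9 lists death, MI, stroke and revascularization for blinded adjudication and does not name CI-AKI. No committee step described in the protocol would therefore catch a wrong sign.

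**Working it through.** **1. The two texts applied to two patients (section 9.7).**
- Preserved output, no creatinine rise: a case under the list, but in no urine stage of the table.
- Output below 0.5 ml/kg/h for 6 to 12 hours, no creatinine rise: not a case under the list, but stage 1 in the table.

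The contradiction lies within one section and needs no outside source.

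**2. The plan's own sizing figure.** The protocol sizes only the primary endpoint (section 10.1): 15% against 10.5% (a 30% reduction), 80% power, 5% level. Section 10 states one-sided tests. With the pooled-variance formula for two proportions and equal arms (assumed):

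n per arm = [1.645 × √(2 × 0.1275 × 0.8725) + 0.842 × √(0.15 × 0.85 + 0.105 × 0.895)]² / 0.045² = 678.2, rounded up to 679, so 1358 in total.

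This matches the protocol. The inflated total of 1385 gives about 692 per arm, used below. None of this involves CI-AKI.

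**3. Dilution under the printed sign.** Let p be the true CI-AKI rate by the creatinine criteria. Let u be the share of patients who meet the urine line as printed, meaning that urine was measured for six hours and was at or above the threshold. Assume u is equal in both arms and independent of creatinine. Then

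observed rate = 1 − (1 − p)(1 − u),

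and a true difference is multiplied by (1 − u). For true rates of 10% and 20% with u = 0.95, the observed rates are 1 − 0.90 × 0.05 = 95.5% and 1 − 0.80 × 0.05 = 96.0%. Ten points become 0.5. At u = 0.80 they become 2 points, and at u = 0.99 they become 0.1.

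**4. Probability of false non-inferiority.** With margin m, 692 per arm, unpooled variance and a one-sided 5% test (the level stated in section 10 for superiority, carried over here as an assumption):

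P = Φ((m − difference)/SE − 1.645).

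Take assumed true rates of 15% (culprit-only) and 20% (complete), so that a 5-point harm is at or beyond each margin below. Worked example for u = 0.95 and m = 3 points: observed rates 95.75% and 96.00%; SE = √(0.9575 × 0.0425/692 + 0.96 × 0.04/692) = 0.0107; P = Φ((0.03 − 0.0025)/0.0107 − 1.645) = 82%.

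| Margin | Table's direction | Printed sign, u = 0.80 | u = 0.90 | u = 0.95 |
|---|---|---|---|---|
| 2 points | 0.1% | 13% | 26% | 50% |
| 3 points | 0.4% | 26% | 52% | 82% |
| 5 points | 5% | 64% | 92% | 99.7% |

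If urine is recorded in fewer patients, the effect shrinks. At u = 0.50 the same formula gives 3%, 7% and 24%. A one-sided 2.5% level lowers the figures but keeps the pattern: for u from 0.80 to 0.95, 7% to 37% with a 2-point margin and 52% to 99% with a 5-point margin.

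The calculation ignores cases defined by oliguria alone, which the printed list would also miss.

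**The case against.** **The sign may be damage from text reading.** The creatinine lines in the same list are visibly corrupted, so the urine sign cannot be taken on trust. This stands as a reason to check the source first. It does not dispose of the point: the urine line shows a valid sign rather than a stray letter, and the signs in the adjacent table read correctly. If the source shows a less-than sign, the point falls.

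**The intended direction is obvious from the table.** All three urine stages require low output, so a careful programmer would probably notice. This stands as mitigation, but the list is the part that defines a case.

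**A reader might infer that nearly every patient becomes a case and that non-inferiority is almost guaranteed.** The protocol does not support that. It prescribes no urine collection, so coverage could be low. At u of 0.80 to 0.90 with margins of 2 or 3 points, false non-inferiority is 13% to 52%: well above the intended error rate, but not assured.

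**A reader might also infer that, with no margin stated and section 10 specifying one-sided tests only for superiority, a non-significant difference is the only available basis for a claim.** That does not follow. Section 10 describes itself as brief, provides for 95% confidence intervals where appropriate, and defers detail to a statistical analysis plan that may well contain the margin and method.

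**Conclusion.** The contradiction within section 9.7 is real as the text reads. If the list is applied literally, the error acts in the anti-conservative direction for the CI-AKI objective in section 5.2. For assumed true rates of 15% and 20% and u of 0.80 to 0.95, the chance of a false non-inferiority conclusion is about 13% to 82% with margins of 2 or 3 points and 64% to 99.7% with 5 points, against 0.1% to 5% with the table's direction.

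These figures rest on assumed CI-AKI rates, margin, urine coverage (equal in both arms and independent of creatinine), equal allocation and test level. The protocol gives no CI-AKI rate, margin or coverage, so the direction is firm and the size is conditional. The consequence is confined to one secondary objective, and the absence of a margin from the protocol is not part of this finding. The point is of moderate weight and worth correcting before CI-AKI is derived.

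**What to change.** 1. Check every comparison sign in the section 9.7 list against the source document, including the creatinine lines, and restore those that are damaged.
2. Reconcile the urine line with the direction of the staging table, so that every patient who is a case by urine output also falls in a urine stage.
3. Confirm that the eCRF field and the derivation code use the reconciled definition before CI-AKI is derived.

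The cost is a few symbols in section 9.7 and one check of the eCRF and code. It needs no extra patients and no change to the primary analysis. The non-inferiority margin can be left to the statistical analysis plan.
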